8.1.1 Solicited Adverse Events

Solicited AEs for this study are pre-specified in Section 8.1.1 and Table 3 of the protocol and include both injection site reactions (ie, bruising, pain, redness, and swelling) and systemic events (ie, chills, diarrhea, fatigue, headache, joint pain, muscle pain, nausea, oral temperature [for assessment of fever], and vomiting) that are reported within seven days following the Day 0 vaccination and are solicited by diary. These events are considered related to the test article and are collected using a severity rating of 0 (Normal), or 1, 2, or 3 (mild, moderate, or severe, respectively), using the maximal severity observed for the specific symptom post-vaccination.

Grading of visible, measurable injection site reactions will be based on the Food and Drug Administration (FDA) Guidance for Industry, Toxicity Grading Scale (TGS) for Healthy Adult and Adolescent Volunteers Enrolled in Preventive Vaccine Clinical Trials (September 2007). Definitions are summarized in Table 4. Notable exceptions include oral temperature, which is collected as a continuous variable and that uses temperature grade ranges established in the toxicity grading scale (TGS) as shown in Table 5, and events of injection site redness and swelling, which will be measured using a Subject Measurement Tool (Appendix 2). Oral temperature (fever) will be summarized by severity according to regulatory guidance, eg, Normal < 38.0°C, Mild = 38.0 - 38.4°C, Moderate = 38.5 - 38.9°C, Severe > 38.9°C. The Subject Measurement Tool is a transparent acetate sheet imprinted with a set of concentric circles with diameters that correspond to TGS ranges that are also used to assign severity.

Table 3: Listing of Diary Solicited Events

Injection Site	Systemic Events			
(local) Events:	General	Gastrointestinal	Respiratory/Facial	
Pain	Oral temperature	Nausea	Eye redness	
Bruising	Chills	Vomiting	Facial swelling	
Redness	Muscle pain	Diarrhea	Eyelid swelling	
Swelling	Joint pain		Hoarseness	
	Headache		Sore throat	
	Fatigue		Cough	
			Difficulty breathing	
			Wheezing	
			Chest tightness	
			Difficulty swallowing	

Note: All events listed will be solicited by diary for 7 days post-dosing. Subjects will report injection site events occurring on the arm where the test article was administered. Events reported outside the solicitation window will be categorized and reported as unsolicited AEs.

Table 4: Definition of Severity Grading for Adverse Events

Severity	Definitions for Local Adverse Events		Definitions for Systemic Adverse Events
Grade	Visual Local AE Size Grading Description	Non-Visual Local AE Grading Description	Systemic AE Grading Description
0 – Normal	Reaction size (greatest single diameter) < 2.5 cm	No noticeable symptom	No noticeable symptom or finding
1 – Mild	Reaction size (greatest single diameter) 2.5 to 5.0 cm	Discomfort or tenderness noticeable, but does not interfere with normal daily activities	Mild symptoms or diagnostic observations; intervention not indicated; no interference with normal activity
2 – Moderate	Reaction size (greatest single diameter) > 5.0 to 10.0 cm	Moderate discomfort or tenderness on firm pressure; causes some limitation of normal daily activities	Moderate symptoms or diagnostic observations; some interference with normal activity, not requiring medical intervention
3 – Severe	Reaction size (greatest single diameter) > 10.0 cm	Severe pain at rest, pain or tenderness immobilizes the injected limb and prevents normal daily activities	Severe symptoms, significantly disrupts or prevents normal daily activities, generally requires medical attention/intervention

Severity Grade	Gast	Fever			
Severity Grade	Nausea	Vomiting	Diarrhea	revei	
0 – Normal	No noticeable symptom	No noticeable symptom			
1 – Mild	No interference with activity, or 1 to 2 episodes/ 24-hour period	r 1 with activity, or 1 (loose) / to 2 episodes/ stools/24-hour		38.0 to 38.4	
2 – Moderate	Some interference with activity, or > 2 episodes/ 24-hour period	Some interference with activity, or > 2 episodes/ 24-hour period	4 to 5 unformed (loose) stools/24-hour period	38.5 to 38.9	
3 – Severe	Prevents daily activity, or requires intravenous hydration	Prevents daily activity, or requires intravenous hydration	≥ 6 loose stools/24-hour period, or requires intravenous hydration	> 38.9	

Table 5: Severity Grade Definition for Solicited Gastrointestinal Adverse Events and Fever

The following summaries of solicited AEs will be presented by treatment group as part of the primary analysis of safety:

- Summary of solicited treatment-emergent AEs by the verbatim terms specified in the diary and within the post-vaccination window (Days 0 6).
- Summary of all local/systemic solicited AEs by severity (mild, moderate, severe), and within the post-vaccination window (Days 0 6).

8.1.2 Unsolicited Adverse Events

Unsolicited adverse events are defined as any adverse events occurring within the 7-day window following vaccination and not specifically solicited in the diary, or any adverse event that occurs outside the 7-day diary solicitation period. The number (percentage) of subjects with unsolicited AEs will be summarized by Medical Dictionary for Regulatory Activities (MedDRA) coded by system organ class (SOC) and preferred term (PT). All unsolicited AEs will be assessed for severity (Section 8.4 in Protocol) and for causality (Section 8.5 in Protocol).

The following summaries of unsolicited AEs will be presented for all subjects in the Safety Population as part of the primary analysis of safety:

- Overall summary of unsolicited AEs by treatment group (Days 0 28).
- A summary by severity (normal, mild, moderate, or severe), MedDRA SOC, PT, and treatment group (Days 0 28).
- A summary by relationship (causality) to test article of an AE (unlikely/unrelated, possibly, probably, or definitely) to test article, MedDRA SOC, PT, and treatment group (Days 0 28).

- A summary of severe and related (unlikely/unrelated, possibly, probably, or definitely) AEs, MedDRA SOC, PT, and treatment group (Days 0 28).
- A summary of any AEs including MAEs, SNMCs and SAEs, by MedDRA SOC, PT, and treatment group (Days 0 28).

The final analysis will include the following summaries of unsolicited AEs.

- Overall summary of unsolicited AEs by treatment group (Days 0 364).
- A summary by severity (normal, mild, moderate, or severe), MedDRA SOC, PT, and treatment group (Days 0 364).
- A summary by relationship (causality) to test article of an AE (unlikely/unrelated, possibly, probably, or definitely) to test article, MedDRA SOC, PT, and treatment group (Days 0 364).
- A summary of severe and related (unlikely/unrelated, possibly, probably, or definitely) AEs, MedDRA SOC, PT, and treatment group (Days 0 364).
- A summary of any AEs including MAEs, SNMCs and SAEs, by MedDRA SOC, PT, and treatment group (Days 0 364).

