Standard severity grading definitions will be provided in the diary. Grading of visible, measurable injection site reactions will be based on the Food and Drug Administration (FDA) Guidance for Industry, Toxicity Grading Scale (TGS) for Healthy Adult and Adolescent Volunteers Enrolled in Preventive Vaccine Clinical Trials (September 2007). Definitions are summarized in Table 5. Oral temperatures will be collected as a continuous variable and graded by the investigator based on ranges provided in the TGS as shown in Table 6.

Investigators will not be required to assess causality of solicited adverse events specifically named in the diary if onset is during the solicitation period (these will be presumed to be treatment-related). Adverse events consistent with the solicited adverse events listed in the diary, but with onset after the solicitation period (ie, Day 7 thereafter), will be captured as unsolicited AEs and are subject to all procedures for unsolicited AE data.

Solicited AEs, collected from the subject diary, which continue after the collection period (ie, on or after Day 7 for vaccination-emergent events) will be followed to resolution. The continuing, solicited AE will be captured by verbatim term on an "AE eCRF" page. The investigators will be required to assess severity of the continuing solicited adverse event(s) starting from the time after the last diary entry until resolution.

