8.1.2 Unsolicited Adverse Events

Any AEs reported spontaneously by subjects will be categorized as unsolicited events and Medical Dictionary for Regulatory Activities (MedDRA) coded by system organ class (SOC) and preferred term (PT). Solicited events with an onset after the solicitation period will also be classified as unsolicited AEs. Unsolicited events that occur within 7 days following vaccination should also be recorded in the subject diary. If any Grade 3 unsolicited event is reported during this period, subjects should be encouraged to contact the investigator by telephone. The investigator may request an *ad hoc* clinic visit at his/her judgment, and should enter any Grade 3 unsolicited adverse event reported by telephone in the unsolicited AE eCRF promptly, even if the balance of diary data is not yet available. All unsolicited AEs will be assessed for severity

(as defined in Section 8.1.2) and for causality (as discussed in Section 8.5), and will be documented in the source documents and captured in the eCRF.

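### Onset, occurrence and time of report are all used to decide when a diary reaction becomes unsolicited, and no rule keeps reactions that continue past Day 6 out of the unsolicited tables

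*SAP*

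**What the plan says.** Three criteria are in use.

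- **Onset.** Protocol 8.1.1 says of diary-type events, "but with onset after the solicitation period (ie, Day 7 thereafter), will be captured as unsolicited AEs". Protocol 8.1.2 repeats the rule: "Solicited events with an onset after the solicitation period will also be classified as unsolicited AEs".
- **Occurrence.** SAP 8.1.2 has two limbs. The first covers events within the 7 days that the diary does not solicit. The second reads "or any adverse event that occurs outside the 7-day diary solicitation period".
- **Report.** The note under Table 3, with the same wording in Protocol 8.1.1 and SAP 8.1.1, reads "Events reported outside the solicitation window will be categorized and reported as unsolicited AEs".

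For a reaction that starts in the diary period and goes on, Protocol 8.1.1 requires follow-up to resolution. It states "The continuing, solicited AE will be captured by verbatim term on an" AE eCRF page, and investigators are "required to assess severity of the continuing solicited adverse event(s) starting from the time after the last diary entry until resolution". The SAP does not mention continuing solicited events.

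On severity, SAP 8.1.1 takes each symptom's maximum after vaccination without giving an end day, and then lists the output as "Summary of all local/systemic solicited AEs by severity (mild, moderate, severe), and within the post-vaccination window", with that window given as Days 0-6. On causality, Protocol 8.1.1 asks for no assessment of named diary events that start in the window, and SAP 12.5 treats a missing relationship as related.

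**The concern.** One reaction can leave two records: a diary entry and an AE eCRF entry. The protocol still calls the second record solicited. The SAP, which governs the tables, never says so, and its own definition turns on when an event occurs. A programmer who applies SAP 8.1.2 literally would put the post-Day-6 record in the unsolicited tables. If its causality field is blank, which Protocol 8.1.1 permits for such events, the record would also appear in the related-unsolicited tables. A Day 0-6 reaction first mentioned at a later visit has the same problem through the Table 3 note.

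Solicited reactogenicity and the 28-day AE profile are both primary safety endpoints, and the Day 28 results may go to regulators in an abbreviated report. If the tabulation rule is still open at unblinding, it will be chosen by people who can see the treatment codes.

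**Working it through.** No figure in the plan depends on this point, so there is none to reproduce. The check sets the rules side by side and then makes a scale estimate.

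**Step 1. Apply each criterion literally to three hypothetical cases.**

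| Case | Onset (Protocol 8.1.1, 8.1.2) | Occurs (SAP 8.1.2) | Reported (Table 3 note, both documents) |
|---|---|---|---|
| A. Injection-site pain starts Day 4, Grade 1 in the diary; still present Day 8, Grade 2 on the AE eCRF; resolves Day 10 | Solicited throughout | Diary record solicited; eCRF record can be unsolicited | Diary record solicited; eCRF record can be unsolicited |
| B. Headache on Day 5, not entered in the diary, first mentioned at Day 28 | Not unsolicited by onset | Not unsolicited | Unsolicited |
| C. Headache starts Day 8 | Unsolicited | Unsolicited | Unsolicited |

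The criteria agree on case C. They can differ on A and do differ on B.

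**Step 2. Look for a rule that settles case A.** Protocol 8.1.1 supplies the second record and its later severity. The SAP has no link between the two records, no flag and no exclusion. SAP 12.5 would code a blank relationship on the second record as related.

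**Step 3. Follow the later severity.** In case A the Grade 2 falls on Day 8. It is absent from the solicited severity table because that table covers Days 0-6, which is the window of the primary endpoint in Protocol 3.2.1. The sentence in SAP 8.1.2 does not cause this. The remaining gap is narrower: the maximal-severity sentence has no end day, and no table is named for severity graded after Day 6.

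**Step 4. Scale.** Inputs:

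- Phase 2 solicited rate for this formulation: 38% (Protocol 1.6.1.1).
- Phase 2 unsolicited rate through Day 28: 18% (Protocol 1.6.1.1).
- Subjects per arm: 1325.
- f, the share of reactors whose reaction continues past Day 6: not given. Protocol 1.8 says only that persistence beyond 7 days is uncommon and not expected. Values of 2%, 5% and 10% are assumed.

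Reactors: 1325 × 0.38 = 503.5.

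Added points if every continuing record were tabulated as unsolicited, and continuation were independent of other unsolicited AEs: 38 × f × (1 − 0.18). With no overlap at all, the upper limit is 38 × f.

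| f (assumed) | Continuing reactors, 503.5 × f | Added points, independent | Unsolicited rate | Upper limit, no overlap |
|---|---|---|---|---|
| 2% | 10 | 0.62 | 18.6% | 18.8% |
| 5% | 25 | 1.56 | 19.6% | 19.9% |
| 10% | 50 | 3.12 | 21.1% | 21.8% |

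**The case against.** The strongest reply is that *occurs* can simply mean *starts*. SAP 12.5 handles partial AE dates by onset. SAP 8.1.1 points back to protocol 8.1.1, the SAP declares itself in accordance with Protocol Version 4.0, and the protocol calls the follow-up record solicited. On that reading no record is counted twice. This stands as far as it goes: a reader might infer that double counting is certain, but no text directs continuing events into the unsolicited tables. It does not remove the ambiguity, because the Table 3 note brings in a third criterion and the SAP is silent on the continuation record. Nor is the fault confined to the SAP, since the protocol carries the same note.

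A reader might also infer that the SAP wording understates solicited severity. It does not. The Days 0-6 cut is the prespecified endpoint, and Protocol 8.4 makes the subjects' own observations the primary data for that period.

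A third tempting inference is that one arm is favoured, because severe solicited AEs in Phase 2 were 3.2% with this formulation and 1.3% with Fluzone HD. Those figures concern severity and not duration. Fluzone HD is not this trial's comparator, Flublok stood at 2.6%, the confidence intervals overlapped, and overall solicited rates were 38% against 37-38%.

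Two further limits hold. Diary events that start in the window are already presumed related, so a blank causality field changes which table the event appears in, not whether it is considered related. And a subject with a continuing reaction is already counted in an all-AE total that includes solicited events, so only the unsolicited tables can move.

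**Conclusion.** The point holds as an unresolved classification rule. Three criteria are in use, they can give different answers for reactions that continue past Day 6 or are first reported late, and the SAP has no rule for the second record. Counting a continuing reaction again as unsolicited is possible, not established. The size is unknown and probably small: the 0.6 to 3.1 point range rests on assumed continuation rates and on independence, and its upper end fits poorly with the protocol's description of persistence as uncommon. No direction between arms follows from the documents. The safety analysis is descriptive, so no test or success criterion is affected. The correction is still worth making, because it concerns primary safety tables, costs little, and is best settled before the Day 28 unblinding.

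**What to change.** 1. In SAP 8.1.2, define an unsolicited AE as (a) a term not solicited in the diary, whatever its onset, or (b) a solicited term with onset on or after Day 7.
2. In the Table 3 note of both protocol and SAP, replace *reported* by *with onset*.
3. Link each AE eCRF record that continues a Day 0-6 solicited event to that event, and exclude it from all unsolicited tables, including those by relationship.
4. Keep the solicited severity table at Days 0-6, and state in SAP 8.1.1 that its maximal severity covers Days 0-6.
5. Add a separate row giving the number and percentage of subjects whose solicited events continued past Day 6, with their maximum later severity.

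The cost is wording, a linking flag on data the protocol already collects, and one extra row of descriptive output. The protocol note would change through an amendment under Protocol 9.5.

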3.2 Trial Endpoints

3.2.1 Primary Endpoints

- Comparative HAI antibody responses (assayed with egg-propagated virus) on Day 28, summarized in terms of the ratio of geometric mean titers (GMTs) AND seroconversion rate (SCR) difference, between subjects receiving Quad-NIV or Fluzone Quadrivalent for all 4 vaccine homologous influenza strains (ie, 2 influenza A and 2 influenza B strains). Non-inferiority for each homologous strain will be demonstrated if:
 - The lower bound of the two-sided 95% CI on the ratio of the GMTs $(GMT_{QuadNIV}/GMT_{Fluzone})$ is ≥ 0.67 ,

AND

• The lower bound of the two-sided 95% CI on the difference between the SCRs $(SCR_{QuadNIV}-SCR_{Fluzone})$ is $\geq -10\%$.

Nanoparticle Influenza	Vaccine, Quadrivalent	Confidential	qNIV-E-301 Protocol
Novavax, Inc.	Version 4	4.0 – 31 October 2019	Page 33

• Number and percentage (95% CI) of subjects with solicited local and systemic adverse events over the 7 days post-injection (ie, Day 0 through Day 6, inclusive); all adverse events through 28 days post-injection (ie, Day 0 through Day 27, inclusive); and MAEs, SAEs, and SNMCs – including AESIs – through 1 year post-injection.

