6.1.8 Day 364 (± 14 days) – Safety Telephone Contact

- Using an IRB-approved script, the trial staff will contact the subjects using a telephone call to query for any MAEs, SAEs, and SNMCs since their last visit, and any concomitant medications taken for these events.
- This visit will mark the end of the trial for the subjects.

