8 TRIAL ASSESSMENT OF SAFETY

8.1 Adverse Events

Adverse events (AEs) are defined as any unfavorable or unintended change in the physical, psychological, or biochemical condition of the subject. An AE temporally related to participation in the trial or due to a procedure performed in the trial, will be documented whether or not considered related to the test article. This definition includes intercurrent illnesses and injuries, and exacerbations of pre-existing conditions. Stable pre-existing conditions which do not change in nature or severity during the trial are not considered AEs; however, these should be collected as part of the medical history. AEs will be considered treatment emergent from the date and time of the first administration of the investigational product.

Data concerning all classes of adverse events will be collected at scheduled visits from the time informed consent is obtained on Day 0 through Day 28, inclusive. After these specified days, data concerning MAEs, SNMCs, and SAEs will be collected (see Sections 8.1.4 and 8.2 for details of these AEs), as well as additional information regarding outcomes/resolutions of AEs reported prior that had no stop date recorded. In addition to the scheduled visits, subjects will be instructed to notify the investigator and/or return to the clinic if any severe AE (solicited or otherwise) or event fulfilling the definition of an SAE occurs at any time following vaccination. If at a scheduled or unscheduled visit, symptoms are presented that would require a physical exam to adequately assess potential AEs, the exam should be performed and vital signs collected. Adverse events will be recorded as observed by the investigator, designated personnel, or as provided by the subject on the diary card or during the in-person visit. Full details of the AE (ie, nature, date of onset, and recovery, as well as an assessment of severity, relationship to trial treatment [unsolicited events only], seriousness, treatment, and outcome) will be recorded in the source documentation and captured in the eCRF, and will generally require the investigator(s) causality assessment, except as discussed below.

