2.2 Study Endpoints

2.2.1 Primary Endpoints

• Comparative HAI antibody responses (assayed with egg-propagated virus) on Day 28, summarized in terms of the ratio of geometric mean titers (GMTs) AND seroconversion rate (SCR) difference, between subjects receiving Quad-NIV or Fluzone Quadrivalent for all 4 vaccine homologous influenza strains (ie, 2 influenza A and 2 influenza B strains).

Non-inferiority for each homologous strain will be demonstrated if:

○ The lower bound of the two-sided 95% CI on the ratio of the GMTs $(GMT_{OuadNIV}/GMT_{Fluzone})$ is ≥ 0.67 ,

AND

- The lower bound of the two-sided 95% CI on the difference between the SCRs ($SCR_{QuadNIV}$ - $SCR_{Fluzone}$) is \geq -10%.
- Number and percentage (95% CI) of subjects with solicited local and systemic adverse events over the 7 days post-injection (ie, Day 0 through Day 6, inclusive); all adverse events through 28 days post-injection (ie, Day 0 through Day 27, inclusive); and MAEs, SAEs, and SNMCs including AESIs through 1 year post-injection.

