APPENDIX 1 – QNIV-E-301 TRIAL PROCEDURES SCHEDULE

Trial Day:	0	3	7	28	90	182	364
Window (days):		± 1	± 1	± 4	± 7	± 7	± 14
Trial Procedures							
Trial Informed Consent	X						
Inclusion/Exclusion Criteria	X						
Medical/Medication History	X						
Physical Exam	X		X [4]	X [4]		X [4]	
Vital Signs	X [1]		X	X		X	
Serology	X			X		X	
PMBC for CMI	$X^{[5]}$		X ^[5]	$X^{[5]}$		$X^{[5]}$	
Trial Treatment Injection	X						
Adverse Event Review [2]	X	X	X	X	X	X	X
Concomitant Medications Review [2]	X	X	X	X	X	X	X
Subject Diary Review				X [3]			
End of Trial							X

Note: Procedures shaded in grey are performed via scripted telephone call.

^[1] Vital signs to be captured pre-vaccination and between 30 to 60 minutes post-vaccination.

^[2] All adverse events and concomitant medications taken will be collected through Day 28; thereafter, only MAEs, SAEs, and SNMCs and medications taken for these events will be collected.

[figure not shown]
^[3] The subject diary will be reviewed by the investigator and collected at the Day 28 visit.

^[4] If needed, a physical examination may be performed, based on the investigator's discretion.

^[5] To be collected from a subset of approximately 140 subjects from several pre-designated clinical sites.

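### The SAP's five Days 0-364 tables of unsolicited AEs mix 29 days of all-AE collection with 336 days of MAE, SAE and SNMC collection only; separately, its 28-day tables run one day past the endpoint

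*SAP*

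**What the plan says.** **Tables.** SAP 8.1.2 defines an unsolicited AE as any event in the diary week that the diary does not name, or any event outside that week. It sets no limit by type of event after Day 28. It then lists five summaries twice. The Days 0-28 set belongs to the primary analysis of safety. The Days 0-364 set belongs to the final analysis and begins with "Overall summary of unsolicited AEs by treatment group (Days 0 364"). The other four are by severity, by relationship, severe and related, and any AE by SOC and PT.

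**Collection.** Protocol 8.1 collects all classes of AE "from the time informed consent is obtained on Day 0 through Day 28, inclusive". It continues: "After these specified days, data concerning MAEs, SNMCs, and SAEs will be collected", together with outcomes of earlier AEs that had no stop date. Note 2 to the schedule in Appendix 1 of the SAP reads "All adverse events and concomitant medications taken will be collected through Day 28; thereafter, only MAEs, SAEs, and SNMCs", and the Protocol's Appendix 1 carries the same note. The Day 90, 182 and 364 contacts (Protocol 6.1.6 to 6.1.8) ask only about these classes; at Day 364 the call is "to query for any MAEs, SAEs, and SNMCs since their last visit".

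**Endpoint.** Protocol 3.2.1 and SAP 2.2.1 count "all adverse events through 28 days post-injection (ie, Day 0 through Day 27, inclusive"), and MAEs, SAEs and SNMCs through one year.

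**Stated split.** SAP 8.1 promises an all-AE profile for 28 days and MAE, SAE and SNMC profiles for one year, tabulated by severity, relatedness, and both together. SAP 8.2 summarises MAEs and SNMCs to Day 364 without giving a layout. SAP 8.3 provides a listing of SAEs to Day 364.

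**The concern.** A table headed Days 0-364 invites the reader to take its percentages as the share of subjects with any unsolicited AE over a year. The trial does not observe that quantity. After the Day 28 visit, a mild event that brings no healthcare visit and leaves no lasting diagnosis is not asked about.

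The overall percentage is therefore too low for its label, and the shortfall is greatest for mild, non-attended terms. The severity and relationship tables also change composition partway through: four weeks of everything, then about 48 weeks of events selected because they were attended, serious or lasting. Nothing in the SAP tells the reader where the change falls.

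The only one-year layouts by severity and causality in the SAP are these mixed tables, since 8.2 gives no layout and 8.3 gives a listing. The one-year MAE, SAE and SNMC component of the safety endpoint thus has no specified severity or causality table of its own, although SAP 8.1 calls for such tabulation.

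**Working it through.** **1. Day counts** (last day minus first day plus 1).
- Endpoint: Day 0-27 gives 27 - 0 + 1 = 28 days. This reproduces the 28 days stated in both documents. The same convention gives 7 days for the diary (Day 0-6).
- SAP primary safety tables: Day 0-28 = 29 days, one day longer (1/28 = 3.6%).
- SAP final tables: Day 0-364 = 365 days.
- All AEs are collected on Days 0-28 (29 days). Days 29-364 are 364 - 28 = 336 days, and 336/365 = 92%.

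The Day 28 visit has a window of ±4 days, so routine all-AE questioning may end anywhere from Day 24 to Day 32 for a given subject.

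**2. Illustration of size.** The inputs are Phase 2 figures from Protocol 1.6.1.1 at the chosen dose: 18% with unsolicited AEs through Day 28 and 7% with MAEs. Assumptions: constant rates, the same rates in this trial, and the MAE rate standing for everything collected after Day 28.
- Daily rate, any unsolicited AE: -ln(1 - 0.18)/28 = 0.00709.
- Daily rate, MAE: -ln(1 - 0.07)/28 = 0.00259.
- Full collection for 365 days: 1 - exp(-0.00709 × 365) = 92.5%.
- As collected: 1 - exp(-0.00709 × 29 - 0.00259 × 336) = 1 - exp(-0.206 - 0.871) = 65.9%.

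Reading the Phase 2 period as 29 days gives 91.8% and 64.6%. Over the Phase 2 groups described there (unsolicited AEs 15-20%, MAEs 6-9%) and both period lengths, the ranges are about 87-95% under full collection and 59-74% as collected.

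**3. The extra day.** With 18% over 28 days, 29 days gives 1 - exp(-0.00709 × 29) = 18.6%, or 0.6 points more. Over the same Phase 2 ranges the gain is about 0.5 to 0.6 percentage points.

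**4. Passages side by side.** The Days 0-364 tables conflict with the collection rule and with SAP 8.1. The Days 0-28 tables agree with the collection rule and conflict only with the Day 27 limit in the endpoint. No passage reconciles either conflict.

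**The case against.** The strongest reply is that the one-year endpoint is already covered. The Days 0-364 set is placed under the final analysis, outside the primary analysis of safety. The one-year primary endpoint is MAEs, SAEs and SNMCs, and SAP 8.2 and 8.3 report these over the right period. A cumulative summary of all recorded AEs is a normal output of a final report, safety is descriptive, and a footnote would cure the label.

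Most of this stands. A reader might infer that the mixed tables are themselves the report of a primary endpoint; the layout of SAP 8.1.2 does not support that. The reply does not remove the gap left by 8.2 and 8.3, which specify no one-year severity or causality tables. A footnote alone would leave the blend in place.

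A reader might also infer a much larger understatement: subtract 7% from 18% to get 11% with only non-attended events, extrapolate that to about 78% over a year (1 - 0.89^(365/28)), and set 78% against 11%. No planned table shows that subgroup. The overall table counts MAEs, SNMCs and SAEs to Day 364, so the relevant contrast is about 66% against 92%, a factor of about 1.4.

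Finally, Protocol 6.2 and 8.1 ask subjects to report severe AEs at any time after dosing, so some other severe events will be recorded after Day 28. Capture is still not systematic, but such events should not be dropped from the tables.

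**Conclusion.** The conflict is real and its consequence is limited. Five planned tables carry a one-year label for a class of events that is routinely collected for 29 of 365 days. Under the constant-rate assumption the overall line would read about 66% where full collection would give about 92% (59-74% against 87-95% over the Phase 2 ranges).

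Those percentages are illustrations. AE rates may fall after the first weeks, subjects differ in how often they report, and SAEs or SNMCs that are not also MAEs would raise the as-collected figure somewhat. The 336 of 365 days does not depend on any of this.

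A reader might infer that the comparison between vaccines is biased. The documents do not support that, because both arms follow the same collection rule. The fault is in labelling and interpretation.

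The mismatch between Day 27 and Day 28 is minor. It would be wrong to conclude that the schedule fails to support Day 28: collection runs through that day, and only the endpoint's parenthesis, "ie, Day 0 through Day 27, inclusive", differs.

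**What to change.** In SAP 8.1.2:

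1. Limit the tables of all unsolicited AEs to the 28-day period, in both the Day 28 review and the final analysis. Choose one end day, 27 or 28, and state it identically in the endpoint, the collection rule and the table titles.
2. Replace the five Days 0-364 tables with the same severity, causality, severe-and-related and SOC/PT layouts for MAEs, SAEs and SNMCs, each separately. These supplement SAP 8.2 and 8.3 and deliver the split stated in SAP 8.1.
3. Put any other AEs recorded after Day 28, such as severe events that subjects report on their own initiative, in a separate table with a footnote that they were not systematically collected.

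The cost is SAP wording and table shells. The common end day also needs a one-line wording change in the Protocol, because its endpoint and its collection rule now differ. No new data or visits are needed.
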